#### ***d. Allocation and Randomisation***

Within 6 hr of fulfilling inclusion criteria, a patient will be randomly allocated either to the prone positioning group or the control group (HFNC alone with no prone positioning therapy). Patients will be randomly allocated to either arm of the study at a ratio based on a 1:1 basis using a REDCAP randomisation process. Randomization will be stratified by site using tables of random permutations using the RECAP database for randomization. The random block length is 4, and random numbers are generated by computer.

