### ***11. Statistical Considerations***

#### ***a. Sample size***

From ICNARC data on patients admitted to ICU with COVID19, 60% required advanced respiratory support. From this, we propose a 60% intubation rate in this cohort as defined above and that proning will decrease it to 40%. From this, 97 patients per group for a beta of 0.2 and alpha 0.05, requiring the need to recruit 196 patients. Interim analysis of data will be conducted using aggregated data as part of the Awake Prone Positioning in COVID Meta-Trial.

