#### ***b. Analysis population***

Data will be analysed on an intention to treat basis with all data for patients who consented to be involved included in baseline data analysis. Outcome data will be analysed for all patients who were positioned in the prone position for any length of time. A further per protocol analysis will be carried out on all patients who tolerated at least 1 hour of the daytime proning time and at least 2 hours of the night time proning period in any 24 hour period. Patients who were rescue prone will be considered a protocol deviation and will be studied as a group. Definition of the two groups: The

patients who receive the prone positioning are classified as prone positioning group. The patients who receive HFNC alone are classified as HFNC group. Comparisons between the two groups: Quantitative continuous variables are given as either means ( $\pm$ SDs) or medians (with inter-quartile ranges) are compared using the unpaired Student's t test or the Mann-Whitney test. Qualitative or categorical variables are compared with the chi square test or the Fisher's exact test. ANOVA for paired tests to compare the same variables collected at different time points are used. The cumulative probability of remaining on spontaneous breathing are compared with the Kaplan-Meier estimate of survival and the log-rank test to compare the two groups. Univariate and multivariate analyses of risk factors for PP failure are performed with logistic regression. All analyses are in intention to treat, and the level of significance is set at 0.05.

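### The plan claims intention to treat, but restricts outcome data to proned patients and defines the compared groups by care received, so patients can leave their randomised arm

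*Combined protocol and SAP*

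**What the plan says.** Section 9d (Allocation and Randomisation) forms the arms by chance: "a patient will be randomly allocated either to the prone positioning group or the control group", the control being high-flow nasal cannula (HFNC) without proning.

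Section 11b (Analysis population) opens by naming intention to treat and closes with "All analyses are in intention to treat". The statements between them are:

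- **Baseline data.** The opening sentence has "all data for patients who consented to be involved included in baseline data analysis".
- **Outcome data.** The next sentence reads "Outcome data will be analysed for all patients who were positioned in the prone position for any length of time".
- **Groups compared.** Of the two groups, "patients who receive the prone positioning are classified as prone positioning group" and "The patients who receive HFNC alone are classified as HFNC group". The list of between-group tests follows directly.
- **Rescue proning.** "Patients who were rescue prone will be considered a protocol deviation and will be studied as a group". The term is not defined.

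The per-protocol analysis is introduced as an additional one, so the any-proning rule reads as the main outcome set and not as a sensitivity analysis. No section says that the outcomes of all randomised patients are compared by allocated arm.

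**The concern.** Three rules in section 11b conflict with the principle that the same section states.

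1. Taken literally, the outcome sentence leaves out every control who was not proned. Taken as a rule for the prone arm only, it still drops patients randomised to proning who were never proned.
2. The comparison groups depend on treatment received, which is decided after randomisation and may depend on prognosis.
3. Rescue-proned patients form a group of their own, and nothing says that they also stay in their allocated arm.

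So a control who is proned could be kept, set apart or counted as prone. A prone-arm patient who is never proned could be kept, dropped or counted as HFNC. These choices give different answers, and the text allows the choice to be made after the data are seen.

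The direction of bias is not fixed. Controls proned because they are worsening carry above-average risk, and removing them from the control group makes proning look worse. But a patient must be alive and not intubated to be proned awake, so proned controls could instead be at below-average risk, and moving them then makes proning look better. Prone-arm patients intubated before a first session have already had the primary event. Dropping them, or counting them as HFNC, favours proning.

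The routes are plausible here. The trial is open label (sections 5a and 9e), patients prone themselves (section 9), and section 9a withdraws those who cannot tolerate 30 minutes.

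**Working it through.** **The plan's own figure.** Section 11a assumes 60% against 40%, alpha 0.05 and beta 0.2. The two-sided formula with pooled variance and no continuity correction gives

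n = [1.960 × √(2 × 0.5 × 0.5) + 0.842 × √(0.6 × 0.4 + 0.4 × 0.6)]² / 0.20² = (1.386 + 0.583)² / 0.04 ≈ 97 per group.

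This matches the stated 97. Twice 97 is 194; the stated total is 196, or 98 per arm. The sample size is not in dispute.

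**Inputs for the illustration**

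- 98 per arm (196/2) and a 60% event rate, both from section 11a. The plan's wording is "we propose a 60% intubation rate in this cohort as defined above"; I apply this rate to the composite primary outcome.
- Assumed: no true effect, so both arms as randomised have 0.60 × 98 = 58.8 expected events.
- Assumed: *m* = 10 or 20 controls are proned, with event risk *r* from 40% to 80%. The documents give neither figure.

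**Formulas**

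- Rate in the remaining controls: c = (58.8 − m·r) / (98 − m). The control arm as randomised stays at 60%.
- Proned controls set apart: shift = c − 0.60.
- Proned controls counted as prone: shift = c − (58.8 + m·r) / (98 + m).
- A positive shift means proning looks better than it is.

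**Worked case, m = 20, r = 0.8**

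- c = (58.8 − 16) / 78 = 0.549.
- Set apart: 0.549 − 0.600 = −5.1 points.
- Counted as prone: the enlarged prone group has (58.8 + 16) / 118 = 0.634, so the shift is 0.549 − 0.634 = −8.5 points.

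Rejection rates are for the chi-square test without continuity correction at two-sided 0.05, by exact summation over the binomial outcomes. As randomised, the rate is 4.9%.

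| m | Risk r | Set apart: shift (points) | Rejection | Counted as prone: shift (points) | Rejection |
|---|---|---|---|---|---|
| 10 | 40% | +2.3 | about 6% | +4.1 | about 9% |
| 10 | 50% | +1.1 | about 5% | +2.1 | about 6% |
| 10 | 60% | 0 | about 5% | 0 | about 5% |
| 10 | 70% | −1.1 | about 5% | −2.1 | about 6% |
| 10 | 80% | −2.3 | about 6% | −4.1 | about 9% |
| 20 | 40% | +5.1 | 10.5% | +8.5 | 22.2% |
| 20 | 50% | +2.6 | about 6% | +4.3 | about 9% |
| 20 | 60% | 0 | about 5% | 0 | about 5% |
| 20 | 70% | −2.6 | about 6% | −4.3 | about 9% |
| 20 | 80% | −5.1 | 10.7% | −8.5 | 22.2% |

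**Prone-arm patients never proned.** By symmetry, dropping 10 to 20 of them corresponds to setting apart, and counting them as HFNC corresponds to counting as prone. The sizes and rejection rates are the same and the signs are reversed: proning looks better if their risk is 80% and worse if it is 40%.

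**The case against.** The best reply is that intention to treat governs. It is stated twice, the group labels echo the arm names in section 9d, and the word receive may be loose wording for allocated to. The literal reading of the outcome sentence would leave no controls to compare, so it can hardly be intended. Beside the per-protocol threshold that follows it, the sentence may only mean that the main analysis sets no minimum dose. Section 9e has the data analysed under coded group labels, which fits analysis by arm. The trial also feeds a meta-trial (sections 5a and 10a), whose analysis plan is not among the documents. Lastly, the top rejection rates need about a fifth of an arm to cross over and a 20-point difference in risk. Section 7c excludes patients unlikely to tolerate proning or in immediate need of intubation, which should keep the never-proned few.

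Part of this stands. The intent is probably intention to treat, and the moderate rows of the table are more plausible than the extreme ones. With only 5 proned controls at 40% or 80% risk, rejection is about 5% if they are set apart and 6% if they are counted as prone.

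It does not settle the text. The no-minimum-dose reading still gives never-proned patients no place in the outcome set. Reading receive as allocated to leaves the status of rescue-proned patients open. Section 9e does not say that the codes follow allocation. A meta-trial plan that was not supplied cannot be assumed to correct this one.

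**Conclusion.** The concern holds. As written, section 11b does not define a single analysis set for the primary comparison, and its working rules contradict the principle it claims. Confidence in the contradiction is high, because it rests on the text alone.

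The size is conditional. If the patients moved have the same risk as the rest, nothing is lost. If their risk differs by 10 to 20 points and they make up about 10% to 20% of an arm, the shift runs from 1.1 to 8.5 points in either direction, against a planned difference of 20 points. False-positive rates run from about 5% to about 22%. These figures show what the wording permits and do not forecast what will happen.

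**What to change.** In section 11b:

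- State that the primary outcome is compared in all randomised patients by allocated arm, whatever proning they received.
- Define both groups by allocation instead of by care received.
- Delete the outcome set based on any proning, or label it supplementary.
- Define rescue proning, and say that these patients stay in their allocated arm, with the separate group kept as a descriptive supplement.
- Report the share of controls proned and of prone-arm patients never proned beside the primary result.

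Ask the sponsor whether the eCRF (appendix B, not supplied) records prone time in both arms; if not, add that item.

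The cost is a wording change and no extra patients. The downside is that the result estimates the effect of allocation to proning, which crossover dilutes. For example, if 10% of controls were proned with full benefit, the control rate would be 0.9 × 60% + 0.1 × 40% = 58%. The difference would be 18 points, and power at 98 per arm would fall from 80.4% to about 72%. That is the price of the principle the plan already claims.

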### **a. Withdrawal criteria**

- Patients cannot tolerate HFNC or prone position for 30 mins
- Patients experience any side effects during prone position, including vomit, dizzy, hypotension, etc.

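### The per-protocol set is selected on proning hours reached after randomisation, with no matching condition for controls, so it has either no comparator or one that is likely, though not certain, to favour proning

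*Combined protocol and SAP*

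**What the plan says.** Section 11b (Analysis population) announces intention to treat and then adds: "A further per protocol analysis will be carried out on all patients who tolerated at least 1 hour of the daytime proning time", joined to a second requirement of "at least 2 hours of the night time proning period in any 24 hour period". Nothing else defines entry to this set. On rescue proning, the next sentence says: "Patients who were rescue prone will be considered a protocol deviation and will be studied as a group". The groups are then described by treatment received: "patients who receive the prone positioning are classified as prone positioning group" and "The patients who receive HFNC alone are classified as HFNC group". The section ends: "All analyses are in intention to treat, and the level of significance is set at 0.05".

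Four other places bear on the point.

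- Section 9d describes the comparator as "the control group (HFNC alone with no prone positioning therapy").
- Section 6a counts invasive ventilation or death from enrolment to day 28, so events in the first hours count.
- Section 9a lists as a withdrawal criterion: "Patients cannot tolerate HFNC or prone position for 30 mins".
- The opening text of section 9 sets a minimum session of 30 minutes, continued for as long as the patient can manage. It defines neither a daytime nor a night-time proning period.

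**The concern.** Entry to the set depends on something that happens after randomisation and that the outcome can prevent. A prone-arm patient who is intubated or dies before completing a daytime and a night-time session cannot qualify, and everyone who does qualify was event-free until then (immortal time). Controls face no such condition: there is no landmark and no requirement to be alive and unintubated through a first night.

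Two readings are possible. On the literal one, controls who received HFNC alone have no proning hours and cannot enter, so no comparison is defined. On the practical one, the analyst sets qualifying prone-arm patients against the whole HFNC-alone group. That removes early failures from one arm only. The same problem would carry into the Kaplan-Meier and log-rank comparison if it were run on this set.

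At stake is whether the per-protocol result can be read as evidence about proning at all. The trial is open label, so the comparator and the entry rule should be settled before outcomes are seen.

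**Working it through.** **The plan's own figure.** Section 11a assumes 60% falling to 40%, alpha 0.05 and beta 0.2, and gives 97 per group. The two-sided pooled formula is n = [1.96·√(2·0.5·0.5) + 0.842·√(0.6·0.4 + 0.4·0.6)]² / 0.20² = 96.9, rounded up to 97. The figure reproduces, so 97 per arm and 60% are used below.

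**Inputs from the documents.** Event rate p = 0.60; 97 per arm (section 11a); 1:1 allocation (section 9d); events counted from enrolment (section 6a).

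**Assumptions not in the documents.** No true effect. All controls kept as HFNC alone. f is the share of prone-arm patients with the event who miss the proning hours. g is the same share among those without the event.

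**Formulas.** The share of the prone arm retained is k = p(1−f) + (1−p)(1−g), and the event rate among those retained is q = p(1−f)/k. The spurious benefit is d = p − q. The chance of a significant result favouring proning, in a two-sided 5% test of two proportions, is approximately Φ[(d − 1.96·se₀)/se₁], where se₀ is the pooled and se₁ the unpooled standard error.

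**One case in full (f = 0.20, g = 0).** k = 0.48 + 0.40 = 0.88, so 97 × 0.88 = 85.4 patients remain. q = 0.48/0.88 = 54.5% and d = 5.5 points. The pooled rate is (58.2 + 46.6)/182.4 = 0.574, giving se₀ = 0.0734 and se₁ = 0.0733. Then (0.0545 − 1.96 × 0.0734)/0.0733 = −1.22, and Φ(−1.22) = 11%.

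**Results at a 60% event rate**

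| f | g | Prone rate | Spurious benefit (points) | Significant, favouring proning |
|---|---|---|---|---|
| 0 | 0 | 60.0% | 0 | 2.5% |
| 10% | 0 | 57.4% | 2.6 | about 5% |
| 20% | 0 | 54.5% | 5.5 | about 11% |
| 33% | 0 | 50.1% | 9.9 | about 26% |
| 30% | 10% | 53.8% | 6.2 | about 13% |
| 20% | 20% | 60.0% | 0 | 2.5% |
| 10% | 30% | 65.9% | −5.9 | 0.3% (about 12% against) |

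Simulated trials agree to within about half a percentage point. At a 40% event rate with g = 0, the first three non-zero values of f give 2.5, 5.2 and 9.1 points and chances of about 5%, 11% and 25%.

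**Direction.** The bias favours proning when f exceeds g. Three features of the plan point that way. Intubation or death before the hours are complete excludes a patient automatically. Withdrawal for intolerance or side effects such as hypotension (section 9a) plausibly falls on sicker patients. Allowing any 24-hour period gives those who stay event-free longer more chances to qualify. The main counterweight is early weaning, which would raise g. It looks limited, because entry S/F is below 94/0.40 = 235 (section 7c) and weaning requires S/F above 340 or P/F above 300 (section 9b). None of this fixes the values of f and g.

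**The case against.** The strongest reply is that the size and the sign both rest on inputs the protocol does not contain. No document says what share of events falls before a day and a night session could be completed. The 33% case implies that 0.60 × 0.33, or about 20% of the arm, is intubated or dead by then, although section 7c excludes patients in immediate need of intubation, with RR above 40, SBP below 80 or multiorgan failure. At 10% the distortion is small. If event-free patients miss the hours as often, the bias vanishes; if more often, it turns against proning. All of this stands, so the figures are an illustration only.

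Four stronger inferences are tempting, and the documents do not support them.

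- A reader might infer that a control proned as rescue would qualify for the set while a compliant control would not. Section 11b sets rescue-proned patients aside as a separate group of deviations.
- A reader might take this to be the plan's only look at patients who took up proning. Section 11b also refers to outcome data in anyone proned for any length of time and groups patients by treatment received. How those sentences fit with intention to treat is a separate question.
- A reader might assume that poor tolerance is expected. The protocol does not say so, and section 7c excludes those likely to be unable to lie prone for 16 hours.
- A reader might conclude that the trial's main result is undermined. This is a supplementary analysis, and its faults do not by themselves invalidate an as-randomised comparison.

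It can also be said that section 11b implies a rule for controls, namely no proning. That is fair, but it supplies no time or survival condition, which is the element that matters.

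**Conclusion.** The concern holds in a limited form. The per-protocol set is selected on hours reached after randomisation, with no matching time or survival condition for controls. It therefore either lacks a comparator or, with the HFNC-alone group as comparator, is biased unless patients with and without the event miss the hours equally often. A bias in favour of proning is the likelier direction but not a certainty.

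Under the null, with all controls kept and only event patients missing the hours, the illustrated distortion is 2.6 to 9.9 points against a planned effect of 20. The one-directional error is about 5% to 26% instead of 2.5%. These figures depend on assumed shares of 10% to 33%. The analysis should be repaired before outcomes are seen, but because it is supplementary the defect does not threaten the trial as a whole.

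**What to change.** State in section 11b that the as-randomised analysis is the main one, and replace the per-protocol rule with a landmark analysis:

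- Pre-specify one time after randomisation and restrict both arms to patients alive and not intubated at that time.
- Classify adherence in both arms using information up to that time only. Rescue-proned controls count as non-adherent controls.
- Count events after the landmark, and adjust for baseline severity.
- Label the result supportive and non-randomised, since restriction on survival and tolerance still selects patients.

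If a complier-average causal effect is wanted instead, with randomisation as the instrument, define uptake as any proning. With the 1-hour-plus-2-hour threshold as the definition, patients below it would still have been proned. That breaks the exclusion restriction and, if proning works, inflates the estimate.

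The daytime and night-time periods used in section 11b must be reconciled with section 9, which defines neither. Which periods or durations are appropriate is for the investigators.

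The cost is mainly wording and a modest additional analysis. Time tolerated prone is already a secondary outcome (section 6b), but the sponsor should confirm that the case report form records clock times well enough to classify patients at the landmark. The price is wider intervals, and events before the landmark are not counted in this supportive analysis.

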# **Awake Prone Positioning to Reduce Invasive VEntilation in COVID-19 Induced Acute Respiratory failure (APPROVE-CARE)**

### *Study Summary*

The coronavirus disease 2019 (COVID-19) outbreak is a pandemic associated with a pneumonia which can worsen rapidly into respiratory failure known as acute respiratory distress syndrome (ARDS). There is a high rate of mortality in patients with severe respiratory failure requiring mechanical ventilation. Adjunctive therapies constitute an important part of the management of early moderate to severe ARDS. In patients with confirmed moderate-severe ARDs receiving invasive mechanical ventilation, prone position promotes lung homogeneity, improves gas exchange and respiratory mechanics permitting reduction of ventilation intensity, and reducing lung injury. Prone positioning has been demonstrated to save lives and is recommended in evidence-based guidelines for the management of moderate-severe ARDS.

The use of proning outside of mechanically ventilated patients to improve gas exchange and reduce the end for invasive ventilation has not been extensively studied outside of case series. Maintaining self ventilation is associated with increased aeration of dependent lung regions, less need for sedation, improved cardiac filling, and better matching of pulmonary ventilation and perfusion and thus oxygenation.

In this protocol, we outline details for a randomized clinical trial to determine whether placing patients who have hypoxemia related to COVID19 into a prone position can improve oxygenation and reduce the requirement for mechanical ventilation. If effective, this simple intervention could be widely and rapidly implemented, potentially reducing the need for ICU admission and invasive ventilation, and potentially even saving lives.

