Contrarily while prone, the dorsal chest wall lifts, the diaphragm shifts similarly to supine position, and the ventral chest wall, now in contact with the firm surface of the bed, is impeded from expanding (8). In the prone position the gravitational forces compress the ventral region, but this effect is damped by regional expansion due to shape matching between lung parenchyma and vertebrae. As the lung mass is anatomically greater in dorsal regions (nondependent when prone) than in ventral region (dependent when prone), the increased aeration and recruitment of the dorsal region tends to exceed the decreased aeration and derecruitment of the ventral regions. That generates a more homogenous ventilation across the entire lung(6). Furthermore, when an individual is supine the heart compresses the medial posterior lung parenchyma (10) and the diaphragm compresses the posterior-caudal lung parenchyma, with the abdominal contents displacing the diaphragm cranially (8,10). Compression by either the heart and/or the diaphragm may exaggerate dependent lung collapse in the supine position (9). During prone ventilation, the heart becomes dependent, lying on the sternum, potentially decreasing medial-posterior lung compression (10). In addition, the diaphragm is displaced caudally, decreasing compression of the posterior-caudal lung parenchyma. A further advantage observed in prone position is both an improvement of ventilation/perfusion match and an increase in cardiac output: the latter is thought to be due to the effect of increased lung recruitment and reduction in hypoxic pulmonary vasoconstriction, resulting in increases in right ventricular preload and decreased right ventricular afterload and a decrease in pulmonary vascular resistance (11,12). An important recent study by Guerin et al. showed that prone positioning applied for at least 16 hours per day in patients with ARDS and  $\text{PaO}_2/\text{FiO}_2 < 150$  mmHg significantly reduced 28-day mortality (16% vs 32%).(15) From currently available evidence, prone positioning may be of value even if there is no improvement in gas exchange [10-14].

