##### **b. Study aim**

The study aims to assess the effect of prone positioning in patients who have hypoxemia related to COVID19 on:

- need for mechanical ventilation
- Improvement in oxygenation as measured by S/F or P/F ratio
- Patient work of breathing as measured by the respiratory distress observation scale
- tolerability of the position as measured by the total number of hours in prone position

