##### **c. Study objectives**

###### **Primary objective**

To assess the effect of awake prone positioning on requirement for mechanical ventilation or death in patients with suspected or confirmed COVID 19 infection.

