## **9. Assignment of intervention**

Awake prone positioning will be performed before or 1 hour after meal. Call bell will be given to the patient and an oxygen probe will be attached to the patient to monitor spO2 during the procedure. Before PP, all the I.V. lines and nasal cannula will be checked by clinicians. Awake prone positioning will be performed by patient under the supervision of clinicians. Assistance will be offered if needed. If tolerated, PP will be maintained for at least 30 minutes, until the patients feel tired to keep that position. Patients will be informed to maintain prone position as long as they can. FIO2 will be adjusted to maintain SpO2 at 92-95%. Protocol for sedation and comfort evaluation during PP: No sedation will be used during the PP on ward. The patients are monitored by bedside respiratory therapist and nurses for their comfort and tolerance for the PP at 5mins, 30 minutes after PP for the first PP in each day.

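### Section 11b sets no cut-off at intubation for rescue proning or for the HFNC-alone group, so a control proned after the primary event could be taken out of the control arm

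*Combined protocol and SAP*

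**What the plan says.** Section 11b (Analysis population) mentions rescue proning once and does not define it: "Patients who were rescue prone will be considered a protocol deviation and will be studied as a group". The same section defines the two groups by treatment received: those who are proned form the prone group, and those who have HFNC alone form the HFNC group. It also says, at its start and again at its end, that analysis is by intention to treat. Its per-protocol set is patients who "tolerated at least 1 hour of the daytime proning time and at least 2 hours of the night time proning period" within any 24 hours.

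Section 4b lists as an aim "tolerability of the position as measured by the total number of hours in prone position". None of these rules states that counting stops at intubation.

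Other sections bear on how they would be read:
- The primary outcome (section 6a) is invasive ventilation or death by day 28.
- The Study Summary, after describing proning in invasively ventilated patients, says: "Prone positioning has been demonstrated to save lives and is recommended in evidence-based guidelines for the management of moderate-severe ARDS".
- Section 3b cites a trial of "prone positioning applied for at least 16 hours per day in patients with ARDS".
- Section 11a assumes 60% intubation without proning and 40% with it.
- The primary objective is "To assess the effect of awake prone positioning on requirement for mechanical ventilation or death", and section 9 says: "Awake prone positioning will be performed by patient under the supervision of clinicians".

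**The concern.** On the protocol's own account, a control who is intubated may then be proned as ordinary ventilator care. That proning comes after the primary event and often because of it. If it makes the patient rescue prone, or means that the patient no longer had HFNC alone, membership of the HFNC group depends on the outcome. Every control removed in this way is a control with an event, so the control event rate falls and the comparison is biased against proning.

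The same missing cut-off touches the per-protocol hours and the section 4b total hours, where time prone on a ventilator could in principle be added to awake time. Those two are weaker parts of the point, for reasons given under the objection.

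**Working it through.** **Plan's own figure.** Section 11a gives 97 per group for 60% v 40%, alpha 0.05 and beta 0.2. With two-sided alpha and pooled variance under the null:

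n = [1.960 × √(2 × 0.5 × 0.5) + 0.842 × √(0.6 × 0.4 + 0.4 × 0.6)]² / 0.20² = 96.9, so 97 per group.

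The figure reproduces. The recruitment target of 196 gives 98 per arm at 1:1.

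**Expected events.**
- Control: 0.60 × 98 = 58.8, taken as 59.
- Prone: 0.40 × 98 = 39.2, taken as 39.

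**Reference comparison, as randomised.** 59/98 (60.2%) v 39/98 (39.8%): uncorrected chi-square 8.16, p = 0.004.

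**Illustration of the literal reading.** Let f be the share of intubated controls who are later proned and set aside from the HFNC arm. The documents give no value for f, so a range is shown. All those removed have had the event, so with m = 59f (rounded to a whole patient) the HFNC rate becomes (59 − m)/(98 − m). The prone arm stays at 39/98.

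| f (assumed) | m removed | HFNC arm left | HFNC rate | p v 39/98 |
|---|---|---|---|---|
| 0 | 0 | 59/98 | 60.2% | 0.004 |
| 10% | 6 | 53/92 | 57.6% | 0.014 |
| 20% | 12 | 47/86 | 54.7% | 0.044 |
| 25% | 15 | 44/83 | 53.0% | 0.075 |
| 50% | 30 | 29/68 | 42.6% | 0.71 |

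In this illustration the result remains below 0.05 up to about one in five intubated controls and is above it at one in four. The bias always runs the same way, because only events are removed.

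**If analysed as randomised.** The comparison stays at 59/98 v 39/98 whatever f is. The fix therefore changes neither the sample size nor the planned power.

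**The case against.** The strongest reply is that the documents do imply a limit. The trial is about awake proning in self-ventilating patients: the objective says so, and section 9 has the patient doing it, with a call bell and no sedation on the ward. The per-protocol rule speaks of hours tolerated in daytime and night-time periods, which is language for awake sessions. The prone-time outcome in sections 4c and 6b ends when the patient asks to turn back or needs emergency repositioning, which hardly fits a sedated, ventilated patient. A deviation is naturally a departure from assigned care, and an intubated control is no longer on HFNC. Section 11b also says that all analyses are by intention to treat.

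Most of this stands. A reader might infer that nothing confines proning to the time before intubation; that goes too far, because the context points the other way. A reader might also infer that ventilated proning would swamp the adherence and hours data, for example by setting 16 hours against the 30-minute minimum session (a ratio of 32). The documents do not support that contrast: section 7c excludes patients unlikely to manage 16 hours on the abdomen, and section 9 asks patients to stay prone as long as they can.

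What survives is narrower. An implied meaning is not an operational rule for several sites working in wards and ICUs. The term rescue prone carries no awake qualifier. The intention-to-treat statement sits in the same section as groups defined by treatment received, so it does not settle where these controls are analysed. The CRF and the meta-trial appendix are not in the documents reviewed, so a definition there cannot be excluded.

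**Conclusion.** The point holds as a gap in the definitions of section 11b that can introduce bias if the wording is followed literally. It does not show that the primary result is compromised: a comparison by randomised arm is untouched.

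The movement in p from 0.004 to between 0.014 and 0.71 rests on three assumptions: the plan's 60% and 40% rates are true; 10% to 50% of intubated controls are later proned; and being studied as a group means removal from the HFNC arm. The second has no source in the documents. The third is one possible reading, which section 11b neither states nor rules out. A reader might infer that the trial is expected to lose its significance; the documents do not support that, and at shares of 10% and 20% the illustration stays below 0.05.

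The per-protocol hours and the section 4b total hours are less exposed, but the same short definition would cover them. The change is worth making because it is cheap and removes a bias of known direction.

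**What to change.** In section 11b:

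1. State that every between-arm comparison is made by randomised arm, and replace the group definitions based on treatment received.
2. Define rescue proning as proning of a control participant before intubation. Keep these participants in the HFNC arm in all comparisons, and report them as a group descriptively only.
3. Count per-protocol hours, and the total prone hours in section 4b, only up to first intubation, death or day 28, whichever comes first.
4. Record proning after intubation separately. It is not a deviation and counts toward none of these measures.

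The cost is a few lines of wording, with no change to sample size or care. It does require intubation times and prone start and stop times. The planned Kaplan-Meier analysis and the prone-time outcome imply that these are collected, but the CRF should be checked to confirm it.
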